5.5.2. Endoscopy

The subject is called to a surveillance endoscopy according to previous planning and undergo a standard upper GI endoscopy in accordance with ESGE guidelines. It can be performed with or without sedation.

Diagnostic endoscopic landmarks for BE will be recorded written and with photo documentation.

Biopsies will be taken according to a strict protocol including biopsies from the cardia. Mapping biopsies will be taken every 2 cm for all endoscopies where BE is discovered (in all 4 quadrants) according to the Seattle surveillance protocol. In addition, endoscopically-suspicious areas will be targeted for biopsies.

After 30 minutes, patients are asked to answer forms about anxiety level and procedure-specific questions to evaluate acceptability. The visual analog scale (VAS) and a quick questionnaire using the adapted ENDOPREM measure will be used.

The pathologist will process and examine each biopsy sample in accordance with standard clinical practice. Cases with dysplasia will be reviewed and discussed with an additional pathologist. When reviewing the biopsy data, the pathologists will be blinded to the result of the EndoSign® test.

Participants will receive a letter from the endoscopist informing them of the endoscopy results in the usual manner.

Clinical Investigation Plan
 Study Code: ES-100
 CIV-ID: CIV-23-06-043373

Follow-up

At follow-up, 7 and 90 days after both EndoSign® test and endoscopy, questionnaires and forms (adapted ENDOPREM, VAS, EQ-5D) will be sent to the patient either by mail or as a survey via REDCap.

5.5.3. When the EndoSign® -TFF3 results arrive, these are filled into the database and a standardized feedback letter is sent to the patient with the test result. Patients will be given the option to phone the nurse administering the test for more information. If the cytology test result indicates atypia or dysplasia (p53 positive), the patient is called for a gastroscopy within 2 weeks and otherwise the patient will continue to be followed according to the previous surveillance regimen.

Adverse events

5.5.4. The research nurse will notify the endoscopist immediately if there is a EndoSign® detachment or other adverse event. A qualified healthcare expert would immediately remove the EndoSign® in the never-reported but theoretically possible case of inhalation.

Subjects receive emergency contact information to be able to quickly make contact in the case of adverse events.

5.5.5. **Flow chart**

Table 1

Procedure	Visit 1 - EndoSign®	Follow-up, 7 day and 90 days	Visit 2 – Gastroscopy	Follow-up, 7 and 90 days
Incl/exclusion criteria	√			
Informed consent	√			
Medical history/ concomitant medications	√			
Patient reported outcome (VAS, ENDOPREM)	√	√	√	√
Questionnaire, EQ-5D	√	√	√	√
Adverse Events	√	√	√	√
Clinical investigation end				√

Clinical Investigation Plan
Study Code: ES-100
CIV-ID: CIV-23-06-043373

6.9 End of the clinical investigation

The clinical investigation ends when the last subject has completed the last follow-up. The sponsor will notify the Swedish Medical Products Agency within 15 days after the end of the clinical investigation and send the clinical investigation report within 1 year after the end of the clinical investigation including an easily understandable summary.

6.10 Biological sampling procedure

6.10.1 Handling, storage, and destruction of biological samples

The TFF3-samples are handled and analysed in accordance with a specified SOP and transported directly from the hospital to the central laboratory (Cyted) in the UK. The samples will be pseudonymized according to the specific clinical performance study identification number. Each sample will be processed using H&E (hematoxylin and eosin) and TFF3 immunohistochemistry. In all cases where atypia is detected, a p53 staining will be performed as an indicator of significant pathology. All samples will be analysed within six months and destroyed immediately after the analysis.

A special material transfer agreement will be drawn up for each hospital so that the samples can be sent and analysed in the UK (outside the EU). This information will also appear in the consent documents.

6.10.2 Biobank

This study is covered by the exception rule in the Biobank Act, which means that the Biobank Act does not apply to samples intended for research and which are analyzed within six months of the time of sampling and destroyed immediately after the analysis. Therefore, no biobank agreement will be signed, and no samples will be registered and/or stored.

6.11 Monitoring plan

The clinical investigation will be monitored by an independent monitor before the clinical investigation begins, during the clinical investigation conduct, and after the clinical investigation has been completed, so as to ensure that the clinical investigation is carried out according to the CIP and that data is collected, documented, and reported according to SS-EN ISO 14155:2020 and applicable ethical and regulatory requirements. Monitoring is performed as per the investigation's monitoring plan and is intended to ensure that the subject's rights, safety, and well-being are met as well as data in the CRF are complete, correct, and consistent with the source data.

Clinical Investigation Plan
Study Code: ES-100
CIV-ID: CIV-23-06-043373

7 Statistical considerations

7.1 Sample size justification

The sample size needs to be in the upper range of what is typical in feasibility studies because the studies are conducted at multiple hospitals. 75 patients in total, or 15 patients per hospital, are considered to be enough to determine the feasibility of EndoSign®. A formal power calculation or sample size calculation is not necessary for this study because accuracy and effectiveness of the technology will not be evaluated.

8 Data management and protection

Data for all subjects who participate in the clinical investigation are coded with a specific clinical investigation identification number. All subjects are registered in a subject identification list (subject enrolment and identification list) that connects the subject's name and personal number with a clinical investigation identification number. All data will be registered, managed, and stored in a manner that enables correct reporting, interpretation, and verification.

8.1 Case Report Form

All data will be anonymized and stored in an electronic study database (e-CRF) using REDCap. The following data will be collected and reported directly in the CRF:

- Sex, age, BMI
- Smoking / Alcohol consumption
- Use of PPI or other acid suppressants
- Year of diagnosis
- Prague classification according to previous endoscopy
- Previous dysplasia
- Previous endoscopic treatments
- Patient-reported experience measurement data (ENDOPREM, VAS)
- Questionnaire results (including EQ-5D)
- EndoSign® -TFF3 test results
- Gastroscopy results (including biopsy results)
- Adverse events

Both written and electronic changes or corrections on CRF will be dated, initialed and explained (if necessary)

8.2 Archiving

The PI and sponsor will maintain the essential clinical investigation documents in the investigation site files archive and sponsor files archive, respectively. The sponsor shall keep all documentation and data for at least years after the clinical investigation has ended. The PI will archive all local investigation documentation for at least 10 years in accordance with Swedish law (Chapter 10, LVFS 2011:19). All documentation and data

Clinical Investigation Plan
Study Code: ES-100
CIV-ID: CIV-23-06-043373

will be stored at the Department of Surgery at Sahlgrenska University hospital, Gothenburg.

8.3 Data protection

If any part of the data is handled by any other organization, inside or outside the European Union, appropriate agreements and/or other documentation will be established, to ensure that the data processing is performed in accordance with the provisions of the General Data Protection Regulation (EU ordinance 2016/679, GDPR) and other relevant legislation, before any data transfer takes place.

The content of the informed consent form shall comply with relevant integrity and data protection legislation. In the subject information and the informed consent form, the subject will be given complete information about how collection, use and publication of their clinical investigation data will take place. The subject information and the informed consent form will explain how clinical investigation data are stored to maintain confidentiality in accordance with national data legislation. All information processed by the sponsor will be pseudonymized and identified with Study-ID.

The informed consent form will also explain that for verification of the data, authorized representatives of the sponsor, as well as relevant authority, may require access to parts of medical records or study records that are relevant to the clinical investigation, including the subject's medical history.

9 Amendments to the CIP

Amendments to the CIP will be agreed upon between the coordinating investigator and the sponsor. Substantial modifications must be approved by the Swedish Ethical Review Authority and/or the Swedish Medical Products Agency (as applicable) before implementation.

10 Deviations from the CIP

Investigator(s) are not allowed to deviate from the CIP except if it is for the protection of the subject's rights, safety, or well-being under emergency circumstances. All such deviations shall be documented and reported to the sponsor, the Swedish Medical Products Agency and/or the Swedish Ethical Review Authority (as applicable) as soon as possible.

All deviations shall be documented with an explanation and reported to the sponsor. Deviations will be reviewed by the sponsor and reported to the appropriate regulatory bodies as required.

Clinical Investigation Plan
Study Code: ES-100
CIV-ID: CIV-23-06-043373

11 Device traceability and accountability

The investigational device(s) will only be used in the clinical investigation and according to the clinical investigation plan. The sponsor provides the site with written instructions and technical support.

The investigator will keep records to document the physical location of all investigational devices from shipment to return/disposal. This record should include: name(s) of clinical investigation personnel who received, used, returned, or disposed the device, the date of receipt, identification and quantity of each investigational device (batch number/serial number or unique code), the expiry date, the date or dates of use, subject study-ID, date on which the investigational device was returned, the date of return of unused, expired or malfunctioning investigational devices, and the date and documentation of disposal of the investigational devices as per instructions of the sponsor.

12 Statements of compliance

12.1 Compliance to the investigational plan, good clinical practice, and regulations

The clinical investigation will be conducted in accordance with GCP, the clinical investigation plan, the ethical principles of the Declaration of Helsinki, the principles of SS-EN ISO 14155:2020 and current national and international regulations governing this clinical investigation. This is to ensure the safety and integrity of the subjects as well as the quality of the data collected.

12.2 Ethical review of the clinical investigation

The clinical investigation will commence when written approval/favorable opinion from the Swedish Ethical Review Authority has been received and at least 30 days has passed since the notification was confirmed by the Swedish Medical Products Agency.

The final version of the informed consent form and other information provided to subjects, must be approved or given a written positive opinion by the Swedish Ethical Review Authority and/or the Swedish Medical Products Agency. The Swedish Ethical Review Authority and the Swedish Medical Products Agency must be informed of any changes in the CIP in accordance with the current requirements.

12.3 Insurance

According to the Patient Injury Act, voluntary subjects are equated with patients. The Swedish healthcare regions have signed a patient insurance with Landstingens Ömsesidiga Försäkringsbolag, LÖF

Clinical Investigation Plan
Study Code: ES-100
CIV-ID: CIV-23-06-043373

13 Informed consent process

13.1 General process for informed consent

The principal investigator shall ensure that the subject is given full and adequate oral and written information about the clinical investigation, its purpose, any risks and benefits as well as inclusion and exclusion criteria. Subjects must also be informed that they are free to discontinue their participation in the clinical investigation at any time without having to provide a reason. Subjects shall be given the opportunity to ask questions and be allowed time to consider the provided information and participation in the clinical investigation. If the person chooses to participate, both the subject and the investigator shall sign the informed consent form. A copy of the subject information as well as a copy of the informed consent form shall be provided to the subject. The subject's signed and dated informed consent must be obtained before performing any activity specific to the clinical investigation. The process shall be documented in the subject's source documents and the signed informed consents shall be maintained with the essential documents. If new information becomes available that can significantly affect a subject's future health and medical care, that information shall be provided to the affected subject(s) in written form. If new information is added to the clinical investigation, the subject has the right to reconsider whether he/she will continue their participation.

14 Adverse events, adverse device effects and device deficiencies

14.1 Definitions

14.1.1 Adverse Event

An Adverse Event (AE) is untoward medical occurrence, unintended disease or injury or any untoward clinical signs, including an abnormal laboratory finding, in subjects, users or other persons, in the context of a clinical investigation, whether or not related to the investigational device.

This definition includes events that are anticipated as well as unanticipated events
This definition includes events occurring in the context of a clinical investigation related to the investigational device, the comparator or the procedures involved.

14.1.2 Adverse Device Effect

An Adverse Device Effect (ADE) is any AE related to the use of an investigational medical device.

This definition includes adverse events resulting from insufficient or inadequate instructions for use, deployment, implantation, installation, or operation, or any malfunction of the investigational medical device.

This definition includes any event resulting from use error or from intentional misuse of the investigational medical device.

This includes 'comparator' if the comparator is a medical device.

Clinical Investigation Plan
Study Code: ES-100
CIV-ID: CIV-23-06-043373

14.1.3 Serious Adverse Event

A Serious Adverse Event (SAE) is any AE that led to any of the following:

- a) death,
- b) serious deterioration in the health of the subject, that resulted in any of the following:
 - i. life-threatening illness or injury,
 - ii. permanent impairment of a body structure or a body function,
 - iii. hospitalization or prolongation of patient hospitalization,
 - iv. medical or surgical intervention to prevent life-threatening illness or injury or permanent impairment to a body structure or a body function,
 - v. chronic disease,
- c) fetal distress, fetal death or a congenital physical or mental impairment or birth defect

14.1.4 Serious Adverse Device Effect

A Serious Adverse Device Effect (SADE) is an ADE that has resulted in any of the consequences characteristic of a serious adverse event.

SAEs related to procedures imposed by the clinical investigation plan but not with the use of the device shall not be considered Serious Adverse Device Effects.

14.1.5 Unanticipated Serious Adverse Device Effect

An Unanticipated SADE is an effect which by its nature, incidence, severity or outcome has not been identified in the current risk assessment. Procedures associated with the use of a device shall be addressed in the risk assessment, which makes it possible to determine whether the procedure related SAEs are Unanticipated Serious Adverse Device Effect or not. SAEs related to procedures imposed by the clinical investigation plan but not with the use of the device shall not be considered Serious Adverse Device Effects.

For the anticipated adverse device effects, see section 4.2 above.

14.1.6 Device Deficiency

A Device Deficiency (DD) is any inadequacy in the identity, quality, durability, reliability, safety or performance of an investigational device, including malfunction, use errors or inadequacy in information supplied by the manufacturer.

14.2 Recording and Reporting

14.2.1 Recording

The principal investigator or an authorized designee will record:

- all AEs
- all SAEs;
- all DDs;
- any new finding in relation to any of the above-mentioned events.

Clinical Investigation Plan
Study Code: ES-100
CIV-ID: CIV-23-06-043373

14.2.2 Reporting

The investigators will report all SAEs and DDs to the sponsor, immediately but not later than 3 calendar days after investigation site study personnel's awareness of the event.

The sponsor will report to the Swedish Medical Products Agency all of the following reportable events:

- any SAE that has a causal relationship with the investigational device or the investigation procedure, or where such causal relationship is reasonably possible;
- any DD that might have led to a SAE if appropriate action had not been taken, intervention had not occurred, or circumstances had been less fortunate; and
- any new findings in relation to any event referred to above.

Reporting by the sponsor will be done by filling out the "Summary Reporting Form" (MDCG 2020-10/2). The form will be filled in/updated for each reportable event or for new findings/updates to already reported events. The form will be transmitted to the Swedish Medical Products Agency. For events that indicate an imminent risk of death, serious injury, or serious illness and that requires prompt remedial action for other patients/subjects, users or other persons or a new finding to it will be reported immediately, but not later than 2 calendar days after awareness by sponsor of a new reportable event or of new information in relation with an already reported event. Any other reportable events or a new finding/update to it will be reported immediately, but not later than 7 calendar days following the date of awareness by the sponsor of the new reportable event or of new information in relation with an already reported event.

14.2.3 Assessment of Causality

The relationship between each adverse event and the investigational device, the comparator and the investigation procedure will be assessed and recorded by the investigator and sponsor. For assessment of causality, the IB and the risk analysis report will be consulted. The sponsor and investigator will distinguish between SAEs related to the investigational device and those related to the procedures, relatedness to both is possible.

Each SAE will be classified according to four different levels of causality:

1. Not related

Relationship to the device, comparator or procedures can be excluded when:

- the event has no temporal relationship with the use of the investigational device, or the procedures related to application of the investigational device;
- the SAE does not follow a known response pattern to the medical device (if the response pattern is previously known) and is biologically implausible;
- the discontinuation of medical device application or the reduction of the level of activation/exposure - when clinically feasible - and reintroduction of its use (or increase of the level of activation/exposure), do not impact on the serious adverse event;
- the event involves a body-site or an organ that cannot be affected by the device or procedure;
- the SAE can be attributed to another cause (e.g. an underlying or concurrent illness/clinical condition, an effect of another device, drug, treatment or other risk factors);

Clinical Investigation Plan
 Study Code: ES-100
 CIV-ID: CIV-23-06-043373

- the event does not depend on a false result given by the investigational device used for diagnosis, when applicable;

In order to establish the non-relatedness, not all the criteria listed above might be met at the same time, depending on the type of device/procedures and the SAE.

2. **Possible**

The relationship with the use of the investigational device or comparator, or the relationship with procedures, is weak but cannot be ruled out completely. Alternative causes are also possible (e.g. an underlying or concurrent illness/ clinical condition or/and an effect of another device, drug or treatment). Cases where relatedness cannot be assessed, or no information has been obtained shall also be classified as possible.

3. **Probable**

The relationship with the use of the investigational device or comparator, or the relationship with procedures, seems relevant and/or the event cannot be reasonably explained by another cause.

4. **Causal relationship**

The SAE is associated with the investigational device, comparator or with procedures beyond reasonable doubt when:

- the event is a known side effect of the product category the device belongs to or of similar devices and procedures;
- the event has a temporal relationship with investigational device use/application or procedures;
- the event involves a body-site or organ that
 - the investigational device or procedures are applied to;
 - the investigational device or procedures have an effect on;
- the serious adverse event follows a known response pattern to the medical device (if the response pattern is previously known);
- the discontinuation of medical device application (or reduction of the level of activation/exposure) and reintroduction of its use (or increase of the level of activation/exposure), impact on the SAE (when clinically feasible);
- other possible causes (e.g. an underlying or concurrent illness/ clinical condition or/and an effect of another device, drug or treatment) have been adequately ruled out;
- harm to the subject is due to error in use;
- the event depends on a false result given by the investigational device used for diagnosis, when applicable;

In order to establish the relatedness, not all the criteria listed above might be met at the same time, depending on the type of device/procedures and the SAE.

14.3 List of foreseeable Adverse events

Foreseeable adverse events*	Incidence (%)	Mitigation and treatment
Adverse events		
Sore throat	44	Conservative treatment, analgesics
Dyspepsia indigestion reflux	13	Conservative treatment, acid suppressants
Oesophageal or gastric pain	11	Conservative treatment, analgesics

Version No: 1.1

Date: 2023-11-29

Clinical Investigation Plan

Study Code: ES-100

CIV-ID: CIV-23-06-043373

Feeling non-specifically unwell	6	Conservative treatment
Nausea or vomiting	6	Conservative treatment, antiemetics
Voice disturbance	3	Conservative treatment
Diarrhea or an upset stomach	4	
Chest pain or discomfort	1	Conservative treatment, analgesics
Allergic reaction	1	Conservative treatment, allergy treatment
Anxiety	1	Conservative treatment
Bad taste	1	Conservative treatment
Paroxysmal positional vertigo	1	Conservative treatment
Blood clot excretion	1	Conservative treatment
Vasovagal attack	1	Conservative treatment
Nosebleed	1	Conservative treatment
Headache	1	Conservative treatment, analgesics
Bloodshot eye	1	Conservative treatment
Chest infection	1	Conservative treatment, antibiotics
Abrasion	1	Conservative treatment
Fall	1	Conservative treatment, orthopedic consultation
Serious adverse event		
Detachment of the sponge on day of the procedure	1	Endoscopy
Hernia	1	Surgery
Myocardial infarction	1	Cardiological treatment
Perforation	N/A	Endoscopic or surgical intervention, conservative treatment, antibiotics
Serious bleeding	N/A	Endoscopic or surgical intervention, blood transfusions

15 Premature termination of the clinical investigation

The sponsor may suspend or prematurely terminate either the clinical investigation at an individual investigation site or the entire clinical investigation for significant and documented reasons. The Swedish Medical Products Agency may suspend or prematurely terminate the clinical investigation at the applicable investigation sites.

If suspicion of an unacceptable risk to subjects arises during the clinical investigation, or when so instructed by the Medical Products Agency, the sponsor will suspend the clinical investigation while the risk is assessed. The sponsor will terminate the clinical investigation if an unacceptable risk is confirmed. The sponsor will inform all investigators.

The sponsor shall consider terminating or suspending the participation of a particular investigation site or investigator in the clinical investigation if monitoring or auditing identifies serious or repeated deviations on the part of an investigator. If the suspension or premature termination was in the interest of safety, the sponsor shall inform all other principal investigators.

If, in the opinion of the investigator, the clinical observations in the clinical investigation suggest that it may be unsafe to continue the investigation at the site, the investigator may terminate participation in the investigation after consultation with the sponsor. A written statement fully documenting the reasons for such termination will be provided to the sponsor. If the clinical investigation is prematurely terminated, the investigators shall promptly inform the subjects and take necessary steps to finalize their engagement in the clinical investigation. All relevant investigation material must be collected, and accountability completed.

If the clinical investigation is interrupted or terminated prematurely the sponsor will report to the Medical Products Agency within 15 days together with a justification. If the sponsor has temporarily halted or prematurely terminated the clinical investigation on safety grounds, the Medical Products Agency will be informed within 24 hours. A clinical investigation report will be prepared within three months of the early termination or temporary halt, irrespective of the results. In the event that the clinical investigation is restarted within three months of the temporary halt, the sponsor does not have to submit a clinical investigation report until the clinical investigation has been completed.

Version No: 1.1

Date: 2023-11-29

Clinical Investigation Plan
Study Code: ES-100
CIV-ID: CIV-23-06-043373

The final clinical investigation report shall include detail with respect to the temporary halt.

16 Publication policy

The clinical investigation will be registered in a publicly accessible database before the start of recruitment activities and the content will be updated throughout the conduct of the clinical investigation and the results entered at completion of the clinical investigation. The results will be presented at national and international scientific meetings and published in scientific journals.

17 Bibliography

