When swallowed and subsequently pulled out of the stomach, it gathers cell samples along its path. These samples are then preserved in a room temperature stable medium. They are subsequently sent to a central laboratory for processing and can be analysed for Barrett's biomarker Trefoil Factor 3 (TFF3), atypia, and stained for p53, which serves as an indicator for dysplasia or cancer.

The EndoSign®'s cell collection, sample processing, and analysis capabilities parallel those of the previously used Cytosponge. Cytosponge-TFF3 test has been shown to detect Barrett's oesophagus effectively. A review of 5 studies underscored the safety and high patient acceptability of this procedure [11]. Remarkably, over 90% of patients succeed in swallowing the Cytosponge on the first try with no serious adverse events reported to date. The risk of detachment is minimal, being less than 1:5,000, and the most common side effect is a sore throat.

Iqbal et al showed in a systematic review that Cytosponge-TFF3 detects Barrett's oesophagus with a sensitivity and specificity of 81% and 91%, respectively. [12]

EndoSign® is a new cell collection device was recently introduced and is currently being evaluated in the Cytoprime 2 project. Based on the equivalency claims to the Cytosponge™ (see Appendix B), the device has been adopted for routine use by National Health Services, England. The EndoSign capsule sponge is:

- Simple for practitioners to use, streamlining training and clinic delivery
- Quick to administer, reducing the time taken for the procedure
- Designed to be easy to swallow, improving patient experience
- Affordable with a cost reduction per unit compared to Cytosponge™
- Safe during withdrawal due to validated and improved mechanical properties of the thread attachment.

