4.2. Objectives and endpoints

Objective	Endpoint	
To assess patient acceptability for EndoSign®	i. EndoSign® test experience compared to upper GI endoscopy ii. EndoSign® swallowing failures iii. Willingness to undergo EndoSign® again	i. Adapted ENDOPREM and a visual analog scale to rate experience ii. Number of patients that are unable to swallow and attempts made iii. Questionnaire
To assess safety of EndoSign® in secondary care	i. Rates of adverse events up to 7 days after EndoSign® test	i. All adverse events reported during procedure, ER-visits and 7-day follow up.
To assess the feasibility of recruitment	i. Proportion of eligible patients who participate ii. Quantify the number of patients that potentially can be recruited	i. Patients accepting invite and consent divided by total of patients invited ii. Number of patients in surveillance per site
To assess the implementation of EndoSign®	i. Costs and resources required to introduce EndoSign® in secondary care ii. Determine technology and equipment needs and training iii. Clinical staff experience and acceptability of EndoSign® in regards of training, skills, reliability, side effects and user information	i. Interviews with staff and healthcare professionals ii. Equipment needed per session iii. Number of sessions needed until fully trained. iii. Interview with clinical staff iv. Number of days from samples are sent to laboratory in UK until test results arrive

Clinical Investigation Plan
 Study Code: ES-100
 CIV-ID: CIV-23-06-043373

	iv. Logistics of TFF3-analysis of EndoSign® and response times	
To evaluate data collection method and outcome measures	i. Feasibility of questionnaires ii. Response rate for questionnaires iii. Withdrawal and drop-out rates iv. Follow-up rates	i. Validate adapted ENDOPREM ii. The proportion of patients who completes each questionnaire iii. The proportion of patients who, for various reasons, do not complete the study iv. The proportion of patients who complete the follow-up

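### Do the 1% entries for serious events in section 14.3, set against the far lower figures in section 2.9, call for a change to the plan?

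*Protocol*

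**What the plan says.** Section 14.3 tabulates foreseeable adverse events with an incidence in percent. Under its serious heading it gives a 1 to "Detachment of the sponge on day of the procedure", to hernia and to myocardial infarction; perforation and serious bleeding carry N/A. The column head for the events has an asterisk, but no matching footnote is visible in the text read for this review.

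Section 2.9 summarises experience with the Cytosponge, the device used before EndoSign. There it states "The risk of detachment is minimal, being less than 1:5,000" and "no serious adverse events reported to date". The passage then turns to EndoSign. It reports adoption by the English health service "Based on the equivalency claims to the Cytosponge", and lists among the new device's features "Safe during withdrawal due to validated and improved mechanical properties of the thread attachment". It gives no numerical detachment rate for EndoSign.

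Section 14.1.5 defines an unanticipated serious adverse device effect as one "which by its nature, incidence, severity or outcome has not been identified in the current risk assessment". It closes with "For the anticipated adverse device effects, see section 4.2 above". The section with that number is headed "4.2. Objectives and endpoints"; the anticipated device effects are listed in section 3.2.

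**The concern.** Two parts of one protocol appear to give incompatible pictures of the device's serious risks. The background offers a very small detachment risk and a clean serious-event record. The safety chapter prints three serious events at 1 in 100 each. The background figures belong to another device, but the protocol leans on equivalence to that device and calls the new thread attachment improved, so a much higher detachment rate for EndoSign would sit awkwardly with the argument.

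Safety is a stated endpoint, measured as adverse event rates up to 7 days. A single detachment among 75 patients would look ordinary against 14.3 and alarming against 2.9. Incidence is one of the grounds in 14.1.5 for calling a serious device effect unanticipated, and the pointer that should lead to the anticipated effects leads to the endpoints table. A further observation is that aspiration, intestinal obstruction and dysphagia appear in 3.2 but not in 14.3. If decisions about safety signals were taken from these figures, the ambiguity would matter.

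**Working it through.** **Inputs.** Detachment at 1%, from 14.3. Detachment below 1/5,000 = 0.02%, from 2.9. Number of patients 75, from 5.1, with one EndoSign procedure each (assumed). The 1% itself cannot be reproduced, because no numerator, denominator or source is visible.

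**Literal reading.**
- Ratio: 0.01 ÷ (1/5,000) = 50. Since 2.9 gives an upper limit, the ratio is at least 50.
- Expected detachments: 75 × 0.01 = 0.75, against at most 75 × 0.0002 = 0.015.
- Chance of at least one: 1 − 0.99^75 = 52.9%, against at most 1 − (1 − 1/5,000)^75 = 1.5%.

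**If 1 is ordinary rounding** of a rate between 0.5% and 1.5%, the ratio starts at 0.005 × 5,000 = 25. At 0.5% the chance of at least one detachment is 1 − 0.995^75 = 31.3%. The figures still disagree. A single observed event would print as 1% for denominators of about 67 to 199.

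**If 1 is a floor**, meaning anything up to 1%, the detachment row is compatible with 0.02% and there is no discrepancy. The table's pattern makes this plausible: of 25 rows, 23 are numeric, 16 of those read 1, and none is lower. So the factors of 25 and 50 hold only under particular readings; across all readings the range runs down to no conflict at all.

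**What uses these figures.** Taking the places where an incidence could affect the trial:
- Unanticipated status (14.1.5) is judged against the current risk assessment, a separate document, and not against 2.9 or 14.3.
- Causality (14.2.3) is assessed with the investigator's brochure and the risk analysis report.
- Reporting to the authority (14.2.2) depends on a causal or reasonably possible link, and on device deficiencies. It sets no separate route for unanticipated effects.
- Suspension or termination (section 15) depends on suspected or confirmed unacceptable risk, with no numerical threshold.
- Sample size (7.1) rests on no formal calculation.
- The safety endpoint (4.2) is the observed event rate; the protocol plans no comparison with the table.

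The estimate would in any case be wide. With no detachments in 75, the one-sided 95% upper limit is 1 − 0.05^(1/75) = 3.9%, which covers both printed figures.

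**Cross-reference.** Section 3.2 carries a title that names exactly what 14.1.5 is looking for. The numbering is visibly displaced elsewhere too: 5.5.5 is followed by 6.9. A reference one chapter too high fits that slip.

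**The case for a change.** The strongest case for acting is that a floor explains detachment but not the other serious rows. The table uses N/A for perforation and bleeding, so a number beside hernia and myocardial infarction suggests that cases were observed, which does not fit a record of no serious events. The edit would be cheap, subjects must be told the risks (13.1), and a safety chapter should not misdirect its reader.

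Part of this stands. As printed, the text does not reconcile the hernia row with 2.9, and the 14.1.5 pointer is plainly wrong. The rest is weaker. The 2.9 statements are explicitly about the Cytosponge, while 14.3 names no device in the text available; the asterisk suggests a note, which may give the source and may have been lost when the document was read. Myocardial infarction is absent from 3.2, and the definition in 14.1.1 covers events whether or not the device caused them, so its presence in a broad list need not contradict a statement that may concern the procedure. The consent pages are not available, so which figures subjects are shown cannot be judged.

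On the omitted events, nothing requires 14.3 to repeat all of 3.2, and the adverse event text in 5.5 already deals with inhalation, describing it as not yet seen. Adding rows without incidences would gain little.

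**Conclusion.** No change to the plan follows. The printed detachment figures differ by a factor of at least 50 if the 1 is a literal percentage for the same or an equivalent device, by 25 or more if it is ordinary rounding, and not at all if it is a floor or comes from a different data set. The document does not settle which, so the conflict is possible but not shown.

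The mismatch does not carry through to the trial. No design choice, analysis, reporting deadline or stopping provision takes its input from 14.3 or 2.9, and the judgement that does depend on incidence is referred to the risk assessment. This conclusion assumes that the risk assessment states its own incidences, which cannot be checked here. The reference to 4.2 is a clerical slip, and a reader who finds the endpoints there can locate 3.2 by its title. A line on the basis of the 1 entries would be a courtesy if the text were being edited anyway; it is not a reason to amend the plan. Confidence in the mismatch as a true contradiction is moderate at most.
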